6.7 Preparation, Reconstitution, and Dispensing

Ixazomib is an anticancer drug and as with other potentially toxic compounds caution should be exercised when handling ixazomib capsules.

6.8 Packaging and Labeling

The study drug ixazomib capsules will be provided by Millennium. The study drug will be labeled and handled as open-label material, and packaging labels will fulfill all requirements specified by governing regulations.

The capsules are individually packaged using cold-form foil-foil blisters that are in a child-resistant carton. There are 3 capsules in each wallet/carton.

6.9 Storage, Handling, and Accountability

Upon receipt at the investigative site, ixazomib should remain in the blister and carton provided until use or until drug is dispensed. The container should be stored at the investigative site refrigerated (36°F to 46°F, 2°C to 8°C). Ensure that the drug is used before the retest expiry date provided by Millennium. Expiry extensions will be communicated accordingly with updated documentation to support the extended shelf life.

Because ixazomib is an investigational agent, it should be handled with due care. Patients should be instructed not to chew, break, or open capsules. In case of contact with broken capsules, raising dust should be avoided during the clean-up operation. The product may be harmful by inhalation, ingestion, or skin absorption. Gloves and protective clothing should be worn during cleanup and return of broken capsules and powder to minimize skin contact.

The area should be ventilated and the site washed with soap and water after material pick-up is complete. The material should be disposed of as hazardous medical waste in compliance with federal, state, and local regulations.

In case of contact with the powder (eg, from a broken capsule), skin should be washed immediately with soap and copious amounts of water for at least 15 minutes. In case of contact with the eyes, copious amounts of water should be used to flush the eyes for at least 15 minutes. Medical personnel should be notified.

6.10 Study Compliance

Not applicable in this study.

6.11 Study Treatment

Schedule of Events and Observations

	Consent	Screening	Ixazomib Administration 3 Hours Before Surgery	Surgery	Postop Day 1	Postop Visit for Staple/Suture Removal
Reference Time Line	14 or fewer days before date of surgery	After consent and prior to ixazomib administration	1 to 3 hours prior to surgical incision	On average a two to four hour period of time with sampling occurring as clinically safe during the tumor resection	Assessment 12 to 36 hours after the end of the surgery	Depending on the nature of the wound repair and integrity staple/suture removal will occur 10 to 20 days after the day of surgery
Patient Education	x					
Laboratory screening		x				
Observation for clinical and laboratory toxicity using standard postop parameters*			x		x	x
Blood sampling just prior to incision				x		
Blood sampling during tumor sampling				x		
Blood sampling during surgical closure				x		
Tumor sampling				x		
* Toxicities are to be assessed according to the NCI Common Terminology Criteria for Adverse Events (CTCAE), version 4.03.						

Informed Consent Process: Patients with recurrent glioblastoma who need surgery will be presented the concept of this study and its pro's and con's. They will then receive a consent form and be allowed to review it. They will then be allowed to ask questions and provided these are satisfactorily answered sign consent. This process may take one or more days.

Screening: After signing informed consent there will be determination of performance status, CBC, Complete Metabolic Panel, Na/K/Glucose/Chloride/Bun/Cr, PT/PTT/INR, Urinalysis, & Serum pregnancy test.

Ixazomib Administration: 4.0 mg Ixazomib administration orally with 8 oz of water 3 hours prior to projected surgery start time. The individual will be observed for evidence of treatment-emergent adverse events. This will be recorded as the on study time. Accurate recording of the time of ixazomib administration will be made in the patient's clinical records.

Surgery: One red top tube of blood will be collected at the time of surgical incision, tumor sampling and wound closure. The time of each sampling will be recorded. The tumor will be sampled at three different sites and the timing of the sampling will be recorded.

Post Op Day 1: General and neurologic exam observations will be collected and laboratory evaluations performed will be collected and recorded.

Post Op Visit for Staple/Suture Removal: The subject will undergo standard staple/suture removal, with observations from the general and neurologic exam being collected for assessment of potential Ixazomib toxicity. The patient will be the off study point and visit (please note that all serious adverse events must be reported up to 30 days after the dose of ixazomib as described in Section 8.2: Procedures for Reporting Serious Adverse Events). The subject will continue to follow-up with their surgeon and oncologist as per standard care for their circumstance and therapy dictates and the adverse events will be captured at those follow-up visits.

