Study Population: Patients with recurrent glioblastoma requiring surgery will be candidates for this study. The specific criteria are as follows: Key Inclusion Criteria 
1. Age 18 or above2. Recurrent glioblastoma for which surgical resection is indicated3. Karnofsky Performance Status of 60 or above4. Platelet count > 100,0005. ANC > 1,5006. Hemoglobin > 9 g/dL7. LFTs < 3 x Upper Limit of Normal for the testing lab8. Creat < 1.5 mg/dL Key Exclusion Criteria 
1. Grade \geq 3 peripheral neuropathy or Grade 2 with pain on clinical examination during the screening period.
Duration of Study: Each individual will begin study activity at the time of Ixazomib administration 3 hours pre-operatively until about two weeks post-operatively when their staples or sutures are removed. It is estimated one subject will be accrued every two months. Thus the study duration will be

approximately 6 months. (please note that all serious adverse events must be reported up to 30 days after the dose of ixazomib as described in Section 8.2: Procedures for Reporting Serious Adverse Events).

STUDY OVERVIEW DIAGRAM

SCHEDULE OF EVENTS

Outline of Events

- I. Informed consent process completed
- II. Laboratory screening to confirm or deny eligibility
- III. Ixazomib administration 3 hours prior to surgery
- IV. Surgical resection of tumor
 - A. Tumor specimen collection for MLN2238 concentration assessment
 - B. Timed blood specimen collection during surgery for MLN2238 concentration assessment
- V. Off-study assessment at the time of suture or staple removal

Safety of ixazomib administration will be assessed from the first administration of ixazomib until approximately 2 weeks post-operatively. Attributions of adverse events will be determined and recorded by likely source of that event.

Schedule of Events and Observations

	Consent	Screening	Ixazomib Administration 3 Hours Before Surgery	Surgery	Postop Day 1	Postop Visit for Staple/Suture Removal
Reference Time Line	14 or fewer days before date of surgery	After consent and prior to ixazomib administration	1 to 3 hours prior to surgical incision	On average a two to four hour period of time with sampling occurring as clinically safe during the tumor resection	Assessment 12 to 36 hours after the end of the surgery	Depending on the nature of the wound repair and integrity staple/suture removal will occur 10 to 20 days after the day of surgery

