2. STUDY OBJECTIVES

2.1 Primary Objectives

1. Measurement of tissue concentration of ixazomib in a glioblastoma after preoperative administration
2. Measurement of blood and plasma concentration of ixazomib during surgical sampling after preoperative administration

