11.3 Pharmacokinetic (PK) Sample Collection and Handling (Mandatory, if Applicable)

Materials and Labeling

Blood samples for PK assessment must be collected in 3-mL Vacutainer tubes containing K2EDTA as the anticoagulant. Resulting blood and plasma PK samples must be stored in plastic storage tubes with caps. No blood collection tubes with separation gel should be used.

Collected tumor samples will be dissected to a size of roughly 200-300 mg. The samples are weighed, wrapped in aluminum foil, and flash frozen on a dry ice acetone bath. The frozen samples are stored at -70 C and shipped on dry ice to the CRO for bioanalysis.

. All containers and tubes must be labeled. The printed information must include the study number, patient identification number, treatment period, and scheduled sampling day and time. No other information will be written on the labels.

Preparation of Plasma Pharmacokinetic Samples

1. Draw blood into labeled and chilled 3 mL lavender top K2EDTA Vacutainer tube.
2. Mix the blood with the anticoagulant by gently inverting the tube 8-10 times and immediately place on wet ice.
3. Centrifuge the blood samples for 10 minutes at 1006g at 4° C in a refrigerated centrifuge within 10 mins of sample collection
4. Immediately following centrifugation, gently remove the plasma from the packed cells and aliquot into two transfer vial filled with lyophilized citric acid. Each aliquot should contain exactly 0.5 mL of plasma.
5. Vortex split tubes thoroughly. Any remaining plasma post split1/split 2 sample aliquots should be discarded following appropriate biohazard disposal procedures.

NOTE: If < 0.5 mL plasma is obtained post centrifugation, do not process or store split1 or split2, record split1: ISV (Insufficient Sample Volume), split2: ISV. If < 1.0 mL plasma is obtained post centrifugation, process and store split1 according to procedure; do not process or store split2, record split 2: ISV. Discard remaining plasma using appropriate biohazard waste disposal procedures.

6. Replace cap on tube and freeze the samples immediately at -70°C

Note: No more than 60 minutes should elapse between blood collection and freezing the plasma samples.

7. Keep samples frozen at -70°C or lower until shipment.

Note: Wet ice is defined as a mixture of ice and water

Radius of rotation (rotor arm length) (cm)	RPM speed needed to achieve 1000g
4	4743
5	4242
6	3873
7	3585
8	3354
9	3162
10	3000
11	2860
12	2738
13	2631
14	2535
15	2449

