Excel formula if rotor length not listed in above table:

$$\text{RPM} = \text{SQRT}((1006 / (0.00001118 * \text{rotor length in cm}))^2)$$

Questions regarding handling the plasma pharmacokinetic specimens should be addressed to the contact person designated by Millennium.

Shipment of Pharmacokinetic Tissue and Blood Samples

All pharmacokinetic samples must be sent to the bioanalytical laboratories specified below in a single shipment at the end of the study or in multiple shipments as agreed upon with the lab (MLN9708 PK samples currently have 618 days of stability and will need to be analyzed before reaching the end of their stability). An inventory list must be included with each shipment. The inventory list must note each specimen drawn for each patient, and note any missing specimens.

The investigator must follow the instructions below:

- For all international shipments, a courier will be designated.
- Notify the bioanalytical laboratories and the designated courier at least 24 hours in

Emory University IRB _____
Takeda Oncology Clinical Study Protocol [X16071]

advance of the planned shipment. Provide the designated courier with the appropriate account number to be used, if applicable.

- Samples should be shipped via overnight delivery only on Monday through Wednesday, excluding holidays.
- Double-bag the frozen samples for each patient in bags that can withstand dry ice conditions.
- Pack the frozen samples in sufficient quantity of dry ice in appropriate containers, to maintain a frozen state for at least 3 days.
- Avoid direct contact between sample bags and dry ice by separating them with a dry ice resistant material (eg, newspaper).
- For all biological samples, follow the International Air Transport Association (IATA) regulations for shipment.
- Ensure that the total package weight does not exceed 27.2 kg (60 pounds).
- Label the package with the sponsor-investigator name and study number.
- Include a return address (which includes the investigator's name) on the outside of each shipping container.
- Comply with all courier regulations for the shipment of biological specimens (include all paperwork).
- Retain all documents indicating date, time, and signature(s) of person(s) making the shipment in the study files.

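### Section 6.11 orders a red top tube for the intra-operative drug-concentration draws, but Appendix 11.3 requires a 3-mL K2EDTA tube for the same blood

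*Combined protocol and SAP*

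**What the plan says.** Section 6.11, in its paragraph on surgery, instructs: "One red top tube of blood will be collected at the time of surgical incision, tumor sampling and wound closure". It asks for the time of each sample to be recorded and gives no tube volume, additive or handling step.

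The Outline of Events in the protocol summary states the purpose of these draws: "Timed blood specimen collection during surgery for MLN2238 concentration assessment". The schedule table, printed in the summary and again in 6.11, lists three intra-operative blood samplings: before incision, during tumor sampling and during closure.

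Appendix 11.3 sets out the PK collection procedure. Under Materials and Labeling: "Blood samples for PK assessment must be collected in 3-mL Vacutainer tubes containing K2EDTA as the anticoagulant". Step 1 of plasma preparation: "Draw blood into labeled and chilled 3 mL lavender top K2EDTA Vacutainer tube". Step 2: "Mix the blood with the anticoagulant by gently inverting the tube 8-10 times and immediately place on wet ice". Step 3 requires the blood to be spun "in a refrigerated centrifuge within 10 mins of sample collection".

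Section 2.1 lists as the second primary objective "Measurement of blood and plasma concentration of ixazomib during surgical sampling after preoperative administration". Section 3.1 includes blood and plasma concentrations in the primary endpoint, and 4.1 sends the surgical blood for assay in both matrices.

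**The concern.** The visit-by-visit text that theatre staff would read and the dedicated PK procedure name different tubes for the same blood. Blood and plasma concentrations are listed primary measurements. Each draw is tied to a moment in the operation after a single dose, so it cannot be taken again. A site working only from 6.11 would breach a mandatory collection requirement in 11.3. Depending on what the red top tube contains, it might also have no sample on which the plasma steps can be carried out.

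**Working it through.** The plan gives no figure to reproduce. The check compares the texts in four steps.

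**1. Are these the same draws?**
- Section 6.11 gives three time points: incision, tumor sampling and closure.
- The schedule table lists three intra-operative blood samplings that match them.
- The Outline of Events gives drug concentration as the purpose, and no other purpose appears for blood taken during surgery.
- No section provides for a separate non-PK tube or for a serum assay of the drug.
- So 6.11 and 11.3 govern the same blood.

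**2. Does Appendix 11.3 apply?** Its heading makes it mandatory where applicable. Sections 2.1, 3.1 and 4.1 all call for blood and plasma concentrations, so it applies.

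**3. Can both instructions be met?**

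| Feature | Section 6.11 | Appendix 11.3 |
|---|---|---|
| Tube | Red top, one per draw | 3-mL Vacutainer (mandatory) |
| Anticoagulant | Not stated | K2EDTA (mandatory) |
| Color and temperature | Red; temperature not stated | Lavender, chilled (plasma step 1) |
| Next step | Record the time | Mix with anticoagulant, wet ice, centrifuge within 10 minutes |

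The mandatory wording in 11.3 is attached to the 3-mL K2EDTA tube. The lavender top and the chilling come from step 1 of plasma preparation. On either element, a single tube cannot satisfy both sections. Neither section refers to the other, and no rule says which prevails.

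**4. Which line should change?** This is an inference, but a strong one. Appendix 11.3 is the complete collection and processing procedure, and its later steps depend on an anticoagulated tube. Section 6.11 mentions the tube in passing. Section 4.1 asks for blood and plasma and does not mention serum.

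**Scope.** 3 draws per patient × 3 patients = 9 planned draws governed by the conflicting text.

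**The case against.** The best case on the other side is that this is a slip with an obvious resolution. Appendix 11.3 is explicit and complete. Its step 1 comes before collection, so anyone preparing the draw from 11.3 meets the K2EDTA tube before the first sample is taken. Patients are dosed at least four weeks apart (4.4), which leaves time to notice an error. Sections 7.1 and 7.1.5 center the study on whether the drug reaches tumor tissue, and those samples do not depend on the blood tube. Section 7.1.3 already provides for replacing a patient whose PK data are missing and irretrievable.

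Much of this stands, and it limits how serious the point is. It does not remove the contradiction. Sections 2.1 and 3.1 still list blood and plasma as primary, and the protection works only if staff consult an appendix that 6.11 does not mention. Replacement under 7.1.3 is a remedy after the loss, and it means dosing another patient before craniotomy.

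A reader might go further and infer that all nine draws, or the primary endpoint itself, would be lost. The documents do not support that. They do not define red top, do not say that a serum result is unusable, and give no likelihood that staff would follow 6.11 over 11.3. Section 11.3 does allow PK samples to go to the laboratory "in a single shipment at the end of the study or in multiple shipments as agreed upon with the lab", so a laboratory check could come late. That shows only that late detection is possible, not that it is expected. Nor does it follow that replacement patients would be needed: 7.1.3 applies only once data are judged irretrievable.

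**Conclusion.** The contradiction holds: one tube per draw cannot be both the red top tube of 6.11 and the K2EDTA tube of 11.3. This rests on the text alone and needs no outside knowledge.

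The consequence is conditional. If staff follow 11.3, no draw is affected. If they follow 6.11, and red top means no anticoagulant (an assumption), each draw so taken would fail to yield the K2EDTA plasma that 11.3 specifies for the plasma endpoint, and could not be repeated. Tumor tissue concentrations are unaffected in either case. The documents give no basis for estimating how many of the nine draws would be involved.

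The change should be made, because it is cheap and concerns a listed primary measurement. The point does not threaten the study's central tissue question, so it rates as should-fix rather than must-fix.

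**What to change.** In 6.11, replace the opening words that name the red top tube with: *Blood for PK, in the K2EDTA tube(s) specified in and processed per Section 11.3*, keeping the rest of the sentence. Pointing to 11.3, rather than repeating a tube count or volume, leaves a single source for the collection details and avoids another amendment if the laboratory's requirements change. The cost is one line of text.

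As a separate item that the same amendment could carry, reconcile the draw times. Section 4.1 gives induction, then one and two hours later; 6.11 and the schedule table give incision, tumor sampling and closure. The two accounts must agree. This mismatch is real, but it is not part of the tube finding and does not add to its weight.

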6.12 Termination of Treatment and/or Study Participation

Patients will be informed that they have the right to withdraw from the study at any time for any reason, without prejudice to their medical care. The investigator also has the right to withdraw patients from the study for any of the following reasons:

- Adverse event
- Protocol violation
- Lost to follow-up
- Progressive disease
- Study terminated
- Other

At the time of withdrawal, all study procedures outlined for the End of Study visit should be completed. The primary reason for patient's withdrawal from the study should be recorded in the source documents and CRF. If the patient is unable to have surgery after the drug

administration or us unable to come to the off study suture/staple removal visit they will be withdrawn from the study and replaced until three patient complete follow-up through the off study visit.

7. STATISTICAL AND QUANTITATIVE ANALYSES

7.1 Statistical Methods

This will be a phase 0 study designed to assess whether or not Ixazomib reaches glioblastoma tissue in measurable concentrations. The drug concentration results and clinical observations after administration will be tabulated and summarized with simple descriptive statistics. The relationship between patient's demographic, tumor and drug concentration results will be assessed with Pearson's correlation coefficient and tested with Wald's test. In addition, the mean and standard error of the concentrations will be estimated using a random-effects model to account for the within-patient correlation of the tumor biopsy samples. Given the limited number of observations, a relatively simple covariance matrix (e.g. compound symmetry) will be assumed.

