7.1.1 Determination of Sample Size

The sample size will be three cases. This is based on clinical judgment believing this will provided enough data to account for tumor inter-tumor heterogeneity. To assist in addressing tumor heterogeneity three samples from different portions of the tumor will be obtained in each case and their location described in the operative report.

Should a patient fail to be able to take the preoperative Ixazomib dose, undergo the surgery for tumor resection, have useful surgical samples obtained or be unable to reach the postoperative visit for suture/staple removal the patient will be removed from study and a replacement patient will be recruited.

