7.1.5 Pharmacokinetics/Pharmacodynamics/Biomarkers (if applicable)

The primary objective of this study is measurement of tumor tissue concentrations of ixazomib in a glioblastoma after preoperative administration. This will be done in one point in time (during surgery) and from multiple spots in the tumor for each of the three participants. The sample from each site within each tumor will be analyzed separately. These results will allow simple descriptive statistics of the concentration data but no formal pharmacokinetic parameters will be calculated.

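### Wald tests of Pearson correlations in three patients: at an assumed 5% level, 30–55% false positives with a normal reference, or 11–16% power (true correlation 0.8–0.9) with t on 1 df; the plan does not say which

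*Combined protocol and SAP*

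**What the plan says.** Section 7.1 begins descriptively: "The drug concentration results and clinical observations after administration will be tabulated and summarized with simple descriptive statistics". It then adds an inferential step: "The relationship between patient's demographic, tumor and drug concentration results will be assessed with Pearson's correlation coefficient and tested with Wald's test". A random-effects model follows, but only for the mean concentration and its standard error; it is not applied to the correlations.

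Section 7.1.1 gives the number of patients: "The sample size will be three cases". The justification is not statistical: "This is based on clinical judgment believing this will provided enough data to account for tumor inter-tumor heterogeneity". Each tumor is sampled at three sites, so nine tumor values are expected from three patients. Replacement does not raise the number of completers, because under section 6.12 patients are "replaced until three patient complete follow-up through the off study visit"; sections 7.1.1 and 7.1.3 also provide for replacement.

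Section 7.1.5 says of the concentration data: "These results will allow simple descriptive statistics of the concentration data but no formal pharmacokinetic parameters will be calculated". The plan gives no significance level, sidedness, standard error, reference distribution, unit of analysis or list of correlations for the test in 7.1.

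**The concern.** A Wald statistic is an estimate divided by its standard error and is ordinarily referred to the normal distribution, which is a large-sample approximation. With three patients there are three independent pairs for any covariate that is constant within a patient, such as age or sex. After a line is fitted, one degree of freedom remains. The normal approximation then has no basis, and the result depends heavily on which standard error the software uses.

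Two analysts could follow section 7.1 faithfully and reach opposite conclusions from the same three points. The risk is that a chance correlation is reported as significant in a study that section 1.9 presents as the step before more advanced phases.

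**Working it through.** **Inputs.** n = 3 patients (7.1.1, kept at three by 6.12). Pearson's r with a Wald test (7.1). Assumed, because the plan is silent: two-sided 5% level, bivariate normal data, the patient as the unit. The plan has no figure of its own to reproduce for this test.

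**Null distribution.** With n = 3 and true correlation 0, r/√(1−r²) follows t on 1 df exactly, so P(|r| > c) = 1 − (2/π)·arcsin(c).

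**Size of the test.** Find the absolute r at which each form rejects, then apply the formula.

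| Reference and standard error | Critical absolute r | False-positive rate |
|---|---|---|
| Normal, √((1−r²)/(n−2)) | 0.8908 | 30.0% |
| Normal, √((1−r²)/n) (maximum likelihood) | 0.7493 | 46.1% |
| Normal, (1−r²)/√n (large-sample) | 0.6514 | 54.8% |
| t on 1 df (cut-off 12.706) | 0.9969 | 5.0% |

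First row in full: c = 1.96/√(1 + 1.96²) = 0.8908, and 1 − (2/π)·arcsin(0.8908) = 0.300. A divisor of n−1 in the first form gives 39.8%, within the same range. A two-versus-one binary covariate also gives 30.0% with the normal reference and 5.0% with t on 1 df. Fisher's z offers no alternative: its variance, 1/(n−3), is undefined at n = 3.

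**Power with t on 1 df** (2,000,000 simulated trials per value).

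| True correlation | 0.3 | 0.5 | 0.7 | 0.8 | 0.9 | 0.95 | 0.99 |
|---|---|---|---|---|---|---|---|
| Power | 5.5% | 6.5% | 8.8% | 11.1% | 16.3% | 23.4% | 48.2% |

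**One data set, four answers.** Take an observed r = 0.90, so 1 − r² = 0.19.

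- Normal, first form: z = 0.90/√0.19 = 2.065, p = 0.039.
- Normal, maximum likelihood: z = 2.065·√3 = 3.576, p = 0.0003.
- Normal, large-sample: z = 0.90·√3/0.19 = 8.20, p < 0.0001.
- t on 1 df: t = 2.065, p = 0.29.

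**If the nine tumor values were pooled as independent.** The plan does not say this would be done. Against a patient-level covariate, with standard error √((1−r²)/7) and an assumed intraclass correlation (ICC), simulation gives these false-positive rates:

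| ICC | 0 | 0.1 | 0.3 | 0.5 | 0.8 |
|---|---|---|---|---|---|
| Normal | 9% | 13% | 21% | 29% | 44% |
| t on 7 df | 5% | 7.5% | 14% | 21% | 37% |

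Pooling therefore does not rescue the test once values cluster within patients. No figure is given for covariates that vary by site within a tumor.

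**The case against.** The plan never says that a normal reference will be used. A t reference on n−2 df is a standard way to test Pearson's r and keeps its 5% size under normality, so the 30–55% range is conditional on a reading of the text. That is fair as far as it goes. But the text names a Wald test, for which the normal reference is the usual one, and the t route leaves a test that rejects only when the three points lie almost exactly on a line. Naming the t reference and the unit of analysis would remove the ambiguity without making the test useful.

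Some limits do stand:

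- The 5% level and normality are assumptions, and the documents do not support normality for drug concentrations.
- The 11–16% power applies only to true correlations of 0.8 to 0.9.
- The n = 3 figures apply to patient-level covariates. Site-level relationships are not quantified, and the pooled calculation describes an analysis the plan does not specify.
- Section 7.1.5 concerns concentration summaries and does not mention correlations, so it supports a descriptive approach only in spirit.

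The consequence is also modest. The primary endpoint (3.1) is the concentrations themselves, the sample size rests on clinical judgment, and neither the stopping rule (7.1.7) nor the safety review (7.1.8) uses these p-values.

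**Conclusion.** The concern holds, and the test is wrong as written. On the normal reference its p-values are badly invalid at n = 3. On t with 1 df they are valid under normality but nearly uninformative. Nothing elsewhere in the plan restricts the test to descriptive use. The sizes quoted rest on an assumed two-sided 5% level, normal data and patient-level covariates. The point should be corrected, but it affects only the supplementary correlations; the primary concentration results and the conduct of the trial do not depend on it.

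**What to change.** In section 7.1, delete the words "tested with Wald's test" with the conjunction before them, and report no p-values for these relationships. Add one sentence: tumor concentrations will be listed and plotted by patient and site, with the blood and plasma values, against the demographic and tumor covariates, and any correlation coefficient will be labelled descriptive with n = 3 patients. This agrees with the descriptive summaries that open section 7.1.

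The cost is one clause removed and one sentence added. No patients or data are affected, and all that is lost is p-values that carry almost no information.
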